### 7.1.1 Molecular pre-screening and screening examination

Only patients with tumors carrying a genetic alteration of ALK are eligible for this study. Patients will be considered potentially eligible if their tumor carries a mutation (including point mutations, insertions and deletions), rearrangement (including translocations and intra-chromosomal rearrangements), or amplification involving the ALK gene, as long as the alteration does not clearly result in inactivation of the kinase activity, such as deletion of the kinase domain, or a stop codon preventing translation of the kinase domain.

If the ALK tumor status is unknown when the patient is initially considered for this study, patients/guardians will be asked to sign the molecular pre-screening ICF. The study sites will pre-screen patients for genetic alterations of ALK by sending a tumor sample to a laboratory designated by Novartis. The tumor sample may be a previously obtained archival sample, or a sample obtained for the purpose of molecular pre-screening for this study (tumor paraffin block or slides). Additionally, a pathology report should be submitted along with the patient's archival tumor block/slides. The ALK analysis results will be communicated to the study center within approximately 2 weeks of receipt of the sample. If the patient is already known to have a genetic alteration of ALK at pre-screening, the laboratory result may be used for eligibility assessment, if Novartis reviews the laboratory assessment and agrees that it is sufficient for eligibility.

#### 7.1.1.1 Molecular pre-screening and screening period

[REDACTED]

[REDACTED]

[REDACTED]

[REDACTED]

[REDACTED]

[REDACTED]

[REDACTED]

[REDACTED]

[REDACTED]

[REDACTED]

[REDACTED]

[REDACTED]

[REDACTED]

[REDACTED]

Patient re-screening is allowed and should be discussed with Novartis on a case by case basis before re-screening procedures are performed.

#### **7.1.1.2 Information to be collected on screening failures**

Patients who sign the molecular pre-screening ICF but do not meet the pre-screening requirements will be considered a screen failure. The reason will be entered on the Screening Log eCRF, and each patient's demographic information will be added to the Demography eCRF. No other data will be entered into the clinical database for patients who are screen failures.

Patients who meet molecular pre-screening requirements and sign the main ICF but do not start treatment for any reason will be considered a screen failure. The reason for not being started on treatment will be entered on the Screening Log eCRF, and each patient's demographic information will be added to the Demography eCRF. No other data will be entered into the clinical database for patients who are screen failures.

#### **7.1.1.3 Patient demographics and other baseline characteristics**

The data that will be collected on patient characteristics at molecular pre-screening and baseline include general demographics, relevant medical history, the diagnosis and extent of their tumor/s and details regarding anti-neoplastic treatments that they have received in the past.

#### **7.1.2 Treatment period**

The treatment period commences on the first day of the first cycle (C1D1) of LDK378 and ends after the last dose of LDK378.

Patients who enter the study will be treated with continuous once daily dosing of oral LDK378 until objective evidence of progression of disease, occurrence of unacceptable toxicities, or patient withdrawal.

During the study treatment period, patients will be regularly monitored to assess the safety and early anti-tumor activity of the treatment. For the purpose of scheduling and evaluations, a treatment cycle will consist of 21 days.

For details of assessments during the treatment period, refer to [Table 7-1](#).

#### **7.1.3 End of treatment visit**

At any time, patients may voluntarily withdraw from the study or be removed from it at the discretion of the investigator. If withdrawal occurs, or if the patient fails to return for visits, effectively withdrawing, the investigator should make a reasonable effort (e.g. telephone, e-mail, letter) to understand the primary reason for a patient's premature withdrawal, record this information on the End of Treatment eCRF, and notify Novartis. Patients may be withdrawn from LDK378 for one of the following reasons:

1. Adverse event(s).
2. Disease progression.
3. Protocol violation/deviation.

4. Patient withdrew consent.
5. Lost to follow-up.
6. Death.

Patients who discontinue LDK378 for any of the above reasons (except death) should be scheduled for an end of treatment (EOT) visit 14 days (up to 21 days) after discontinuing LDK378, at which time all of the assessments listed for the EOT visit will be performed. An EOT eCRF will be completed, giving the date and reason for stopping the LDK378.

The EOT completion evaluations include the following:

- A physical examination, including an assessment of any tumor lesions; Karnofsky/Lansky performance status; height/weight and vital signs; hematology; chemistry; pregnancy test for FCBP.
- Radiological tumor evaluation of all tumor sites, if not evaluated  $\leq 28$  days prior to the EOT visit, and if objective evidence of disease progression has not previously been documented.
- For neuroblastoma patients: MIBG imaging, if positive at baseline and not evaluated  $\leq 28$  days prior to the EOT visit.
- For neuroblastoma and lymphoma patients: If bone marrow bilateral aspirate and biopsies were performed and were positive at screening, it will be left to the investigator's discretion to monitor the bone marrow aspirate at each disease evaluation. In order to confirm a Complete disease Response (CR), bone marrow biopsy or aspirate may be required when a radiological CR has been achieved.
- ECG.
- Occurrence of new AEs and status of current AEs.
- Collection of a fresh tumor biopsy, if medically feasible, and the patient and/or guardian agrees.

All patients who discontinue LDK378, including those who refuse to return for a final visit, should be contacted 30 days (up to 37 days) after discontinuing LDK378 for safety evaluations and a list of concomitant medications, including antineoplastic therapies received since discontinuation (Study Evaluation Completion (SEC) visit). See [Section 7.1.4](#). A SEC eCRF will then be completed, giving the date and reason for study discontinuation.

For patients who refuse to return for visits or are unable to do so, every effort should be made to contact them or a knowledgeable informant by telephone. Patients lost to follow up should be recorded as such on the Study Evaluation Completion eCRF. A patient is considered "lost-to-follow up" if the patient fails to show up for a scheduled follow-up visit and no response despite at least 3 documented failed attempts to contact the patient, such as via phone calls and / or registered letters. The investigator should show "due diligence" by documenting in the source documents steps taken to contact the patient (e.g., dates of telephone calls, registered letters, etc).

Patients whose treatment is interrupted or permanently discontinued due to an AE must be followed until resolution or stabilization of the event. Patients requiring interruptions greater than 2 cycles (42 days) will be discontinued from study treatment. In certain cases, if the Investigator and the Sponsor conclude that a patient, who has experienced a treatment

interruption greater than 2 cycles (42 days), could benefit from additional treatment, continuation may be allowed.

Patients who discontinue from the study for a study-related adverse event will be followed for toxicity, as described above. All patients should be followed for adverse events and serious adverse events for 30 days (up to 37 days) following the last dose of LDK378 (Study Evaluation Completion (SEC) visit).

Patients who discontinue from LDK378 (e.g., due to disease progression) during Cycle 1 should have all the remaining evaluations for Cycle 1 performed prior to LDK378 completion. The EOT visit is not considered the end of the study.

### **7.1.3.1 Patient replacement**

#### **Escalation:**

Patients will not be replaced on study. However, if a patient is considered as non-evaluable for the DDS (Dose Determining Set), enrollment of a new patient to the current cohort will be considered if there is less than the required number of evaluable patients. Enrollment of new patients may be considered until at least the minimum number (3) or at most the maximum number (6) of evaluable patients is achieved within the cohort. Minimum and maximum numbers of evaluable patients per cohort are defined in [Section 6.2.3](#).

#### **Expansion:**

Patients will not be replaced.

### **7.1.3.2 Withdrawal of Consent**

Patients may voluntarily withdraw consent to participate in the study for any reason at any time. Withdrawal of consent occurs only when a patient does not want to participate in the study any longer, and does not allow further collection of personal data.

In this situation, the investigator should make a reasonable effort (e.g. telephone, e-mail, letter) to understand the primary reason for the subject's decision to withdraw his/her consent and record this information.

Study treatment must be discontinued and no further assessments conducted, and the data that would have been collected at subsequent visits will be considered missing.

Further attempts to contact the subject are not allowed unless safety findings require communicating or follow-up.

All efforts should be made to complete the assessments prior to study withdrawal. A final evaluation at the time of the subject's study withdrawal should be made as detailed in the assessment table. Novartis will continue to keep and use collected study information (including any data resulting from the analysis of a subject's samples until their time of withdrawal) according to applicable law.

All biological samples not yet analyzed at the time of withdrawal will no longer be used, unless permitted by applicable law. They will be stored according to applicable legal requirements.

#### **7.1.4 Follow-up period**

All patients will have a Study Evaluation Completion (SEC) visit 30-days (up to 37 days) after the last dose of LDK378. At this time AE, SAE and concomitant medication (including subsequent antineoplastic therapy) information during the follow-up period will be recorded on the AE eCRF and Novartis will be informed as necessary.

Patients lost to follow-up should have this documented on the appropriate eCRF and attempts made to contact the patient to ascertain the reason and required study information, as described in [Section 7.1.3](#).

#### **7.1.5 Lost to follow-up**

For patients whose status is unclear because they fail to appear for study visits without stating an intention to withdraw consent, the investigator should show "due diligence" by contacting the patient, family or family physician as agreed in the informed consent and by documenting in the source documents steps taken to contact the patient, e.g. dates of telephone calls, registered letters, etc. A patient should not be considered lost to follow-up until due diligence has been completed. Patients lost to follow up should be recorded as such on the appropriate eCRF page.

### **7.2 Assessment types**

#### **7.2.1 Efficacy**

Disease will be assessed as per RECIST v1.1 ([Appendix 5](#)) in patients with solid tumors, and per IWG criteria ([Appendix 6](#)) for patients with lymphoma. In addition, patients with neuroblastoma will be assessed by MIBG scanning and bone marrow bilateral aspirate and biopsy at screening. Disease response and progression will be determined by the local investigator. When the revised International Neuroblastoma Response Criteria (INRC) currently in development are final they will be incorporated into this protocol.

At screening (within 28 days of the start of LDK378), all patients will undergo CT with i.v. contrast or MRI of the brain, chest, abdomen and pelvis. If there is clinical evidence of disease in the neck, a CT or MRI of the neck will also be performed. If a patient is intolerant of iodine-based contrast agents, CTs may be performed without contrast or MRI may be used. Visible skin lesions and easily palpable subcutaneous tumors may be measured by physical examination using a ruler or calipers. Ultrasound should not be used to measure sites of disease. Patients with neuroblastoma will undergo MIBG scanning, and bone marrow bilateral aspirate and biopsy at screening. Patients with lymphoma will undergo bone marrow bilateral aspirate and biopsy at screening. MIBG scans should be performed within 28 days of the start of treatment, and bone marrow bilateral aspirates and biopsies should be performed within 42 days of the start of treatment.

Subsequent disease evaluations will be performed on Day 15 ( $\pm 7$  days) of cycles 2, 4 and 6. After cycle 6, disease evaluations will be performed on Day 15 ( $\pm 7$  days) of every 4th cycle (e.g., C10, C14), or sooner if there is clinical evidence of disease progression. Post Cycle 14, disease evaluations will be performed every 6 cycles (e.g., C20, C26, C32, etc.) and also performed at EOT. If the last prior disease evaluation was within 28 days of EOT or objective evidence of progressive disease has already been documented, then evaluations do not need to be repeated at EOT.

Disease evaluations after the screening assessment will include evaluation of all sites of disease identified at baseline, using the same technique that was used at screening. If there was no evidence of disease in a body region at baseline, that region does not need to be imaged at subsequent assessments, unless there is clinical concern for a new lesion in that body region. Bone marrow bilateral aspirate and biopsies, and MIBG scans are not required after screening if they were negative at screening. If bone marrow bilateral aspirate and biopsies were performed and were positive at screening, it will be left to the investigator's discretion to monitor the bone marrow aspirate at each disease evaluation. In order to confirm a Complete disease Response (CR), bone marrow biopsy or aspirate may be required when a radiological CR has been achieved.

MIBG scans if positive at screening will be required at each disease evaluation unless 2 consecutive MIBG scan post screening were negative and tumor response is a confirmed Complete or partial response. MIBG scan will be required if radiological assessment demonstrates a progression of the disease.

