### 10.7.3 Efficacy

Anti-tumor activity of LDK378 will be evaluated using investigator-assessed tumor response based on RECIST 1.1 for patients with neuroblastoma and other solid tumors, and IWG

[REDACTED]

criteria for patients with lymphoma, and summarized in terms of overall response rate (ORR), duration of response (DOR), and progression-free survival (PFS). In patients with neuroblastoma, disease assessable only by MIBG scans and by bone marrow evaluation at screening will be treated as non-target lesions. When the revised International Neuroblastoma Response Criteria (INRC) currently in development are final they will be incorporated into this protocol.

For analysis by treatment group, patients from the expansion part and patients from the escalation treated at the MTD/RDE on the same regimen (either fasted or fed) will be combined to be included in the same dose level.

For analysis of patients at the MTD/RDE on one regimen (either fasted or fed), patients from the dose escalation part treated at the MTD/RDE on the same regimen will be classified into one of the expansion groups.

For patients with neuroblastoma, resolution of disease assessable by MIBG scans will also be summarized by treatment group separately from the response assessment by RECIST 1.1.

ORR will be summarized by treatment group and by expansion group, and exact 95% confidence intervals will be presented. To assess anti-tumor activity in pediatric patients previously treated with an ALK inhibitor, BOR and ORR will be tabulated for this subset of patients.

Kaplan Meier analyses of PFS and DOR will be provided overall and by treatment group, if sufficient number of patients allow. For MTD/RDE patients, Kaplan Meier analyses of PFS and DOR will be done by expansion group, if appropriate.

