### 2.4.3 Determination of non-target lesion response

**Table 2-2 Response criteria for non-target lesions**

| Response Criteria         | Evaluation of non-target lesions  |
|---------------------------|---|
| Complete Response (CR):   | Disappearance of all non-target lesions. In addition, all lymph nodes assigned a non-target lesions must be non-pathological in size (< 10 mm short axis)   |
| Progressive Disease (PD): | Unequivocal progression of existing non-target lesions.   |
| Non-CR/Non-PD:            | Neither CR nor PD   |
| Unknown (UNK)             | Progression has not been documented and one or more non-target lesions have not been assessed or have been assessed using a different method than baseline. |

 Although a clear progression of non-target lesions only is exceptional, in such circumstances, the opinion of the treating physician does prevail and the progression status should be confirmed later on by the review panel (or study chair).

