**Table 2-3 Overall lesion response at each assessment**

| Target lesions | Non-target lesions         | New Lesions | Overall lesion response |
|----------------|----------------------------|-------------|-------------------------|
| CR             | CR                         | No          | CR          |
| CR             | Non-CR/Non-PD  | No          | PR                      |
| CR, PR, SD     | UNK                        | No          | UNK                     |
| PR             | Non-PD and not UNK         | No          | PR          |
| SD             | Non-PD and not UNK         | No          | SD       |
| UNK            | Non-PD or UNK              | No          | UNK         |
| PD             | Any                        | Yes or No   | PD                      |
| Any            | PD                         | Yes or No   | PD                      |
| Any            | Any                        | Yes         | PD                      |

. This overall lesion response also applies when there are no non-target lesions identified at baseline.

. Once confirmed PR was achieved, all these assessments are considered PR.

. As defined in [Section 2.4](#).

If there are no baseline scans available at all, then the overall lesion response at each assessment should be considered Unknown (UNK).

If the evaluation of any of the target or non-target lesions identified at baseline could not be made during follow-up, the overall status must be ‘unknown’ unless progression was seen.

In some circumstances it may be difficult to distinguish residual disease from normal tissue. When the evaluation of complete response depends on this determination, it is recommended that the residual lesion be investigated (fine needle aspirate/biopsy) to confirm the CR.

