### 3.5.2 Overall disease response

If a patient has an overall radiological response of CR as defined in [Table 14-16](#), then this response must be confirmed by bone marrow biopsy or aspirate (if required as per the Study Protocol), presence of normal liver and spleen size, and evaluation of lymphoma related B-symptoms. The patient's overall response will be calculated as follows (see also [Appendix D](#)):

A patient will be deemed to have overall disease response of CR if bone marrow biopsy or aspirate becomes negative for tumor involvement (if the bone marrow was involved by lymphoma at baseline) and the liver and spleen are normal in size and there are no lymphoma related B-symptoms in addition to radiological CR.

If assessments of any of the following: lymphomatous infiltration of bone marrow (If required as per the Study Protocol), or evaluation of B-symptoms is not done, unknown or indeterminate or B-symptoms are still present when the overall radiological response is assessed as CR or the liver or spleen are enlarged, then the overall disease response will be assessed as PR until evaluation of these factors have shown normalized results and recorded on the corresponding CRF.

For patients whose radiological response is anything other than CR, assessment of bone marrow, liver, spleen and B-symptoms will not be required in evaluating overall response and overall disease response is the same as radiological response. However any new or recurrent bone marrow involvement at any time during follow-up will be considered PD.

Of note, appearance of B-symptoms or enlarged spleen or liver will not in themselves constitute documentation of progression. They are however expected to be associated with progressive disease. Every effort should be made to document that evidence radiologically and report the corresponding tumor assessments. Such tumor assessments are expected to be performed within 2 months of appearance of B-symptoms or enlarged spleen or liver.

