2.6 Analysis^[SP1] of the secondary objectives

A secondary objective of this study is to assess the anti-tumor activity of LDK378 in fasting and fed states. The primary evaluation of the anti-tumor activity of LDK378 will be based on investigator assessment of response (Overall Response Rate, Progression-Free Survival, and Duration of Response) using the FAS per RECIST 1.1 for patients with neuroblastoma and other solid tumors, and IWG criteria for patients with lymphoma. In patients with neuroblastoma, disease assessable at screening only by MIBG scans and by bone marrow evaluation will be treated as non-target lesions. MIBG response will be listed.

Overall Response rate

ORR is defined as the proportion of patients with a best overall response (BOR) of complete response (CR) or partial response (PR) for RECIST. For CHESON: The evaluation of overall disease response at each assessment is a composite of the individual radiological responses (index and non-index lesions, new lesions), laboratory test (bone marrow) and clinical responses (lymphoma related clinical symptoms). ORR will be summarized by indication and by treatment group, where the patients are pooled from both the dose escalation and expansion phases for MTD / RDE determined for each regimen, and exact 95% confidence intervals will be presented.

In addition, for the expansion group patients with ALK activated neuroblastoma, a Bayesian approach will be used to estimate the ORR based on RECIST 1.1 data, along with a 95% credible intervals based on the posterior distributions, using minimally informative unimodal Beta prior distributions. The prior clinical assumption for LDK378 in this selected patient population will be used in order to derive a minimally informative unimodal Beta prior distribution that reflects the level of uncertainty around the ORR before starting the current trial. At completion of the study, this prior distribution will be updated with all data available from the expansion group patients with ALK activated neuroblastoma (including those treated at the MTD in the dose escalation part) in the FAS. Once updated, the posterior probability that the true ORR at the MTD/RDE for these patients lies in the following categories will be presented:

- [0, 10%) insufficient antitumor activity.
- [10%, 20%) limited antitumor activity.
- [20%, 30%) moderate antitumor activity.
- [30%, 100%] substantial antitumor activity.

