Partial or complete responses reported prior to any additional anticancer therapy will be considered for ORR computation irrespective of the number of missed assessments before response. In this section, the 'missing adequate assessment' is defined as assessment not done or assessment with overall lesion response equal to UNK. For the sake of simplicity, the 'missing adequate assessment' will also be referred as 'missing assessment'.

As detailed in Section 14 (Appendix 5 and 6) of the LDK378X2103 protocol, the PFS censoring and event date options depend on the presence and the number of missing tumor assessments. *For example, an event occurring after two or more missing assessments is censored in the analysis of PFS at the last adequate tumor assessment before the event date.*

An exact rule to determine whether there is none, one or two missing assessments is therefore needed. This rule will be based on the distance between the last adequate tumor assessment date and the event date.

If the distance is larger than threshold D_1 or D_2 then the analysis will assume one or two missing assessments, respectively. The threshold D_1 will be defined as the protocol specified interval between the tumor assessments plus the protocol allowed window around the assessments. Similarly, the threshold D_2 is defined as two times the protocol specified interval between the tumor assessments plus the protocol allowed window around the assessments. For example, in this study, the protocol defined schedule of tumor assessment is every 6 weeks for the first six cycles, and each assessment is expected to be performed at the scheduled time point plus or minus 1 week, i.e. the window is 2 weeks, then any distance larger than $D_1 = 6+2 = 8$ weeks means one missing assessment and any distance larger than $D_2 = (2*6) + 2 = 14$ weeks means two missing assessments. Please see protocol 7.1 for the complete schedules for tumor assessments.

The same definition of D_2 will be used to determine the PFS censoring reason. Possible censoring reasons for PFS are:

- 1: Ongoing without event
- 2: Lost to follow-up
- 3: Withdrew consent
- 4: Adequate assessment no longer available
- 5: New cancer therapy added
- 6: Event after ≥ 2 missing tumor assessments

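### In neuroblastoma, marrow disease is a RECIST non-target lesion but repeat marrow is optional, so a target-lesion PR or SD can be scored unknown and ORR depends on how each site reads the rule

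*Protocol*

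**What the plan says.** **Status of marrow disease.** Protocol 10.7.3 says that in neuroblastoma "disease assessable only by MIBG scans and by bone marrow evaluation at screening will be treated as non-target lesions". SAP 2.6 repeats this for disease assessable at screening only by MIBG and "by bone marrow evaluation will be treated as non-target lesions".

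**Schedule.** When marrow is positive at screening, Protocol 7.2.1 leaves it to the investigator's "discretion to monitor the bone marrow aspirate at each disease evaluation". Table 7-1 makes repeat marrow optional unless there is a radiological CR. The same paragraph of 7.2.1 also says that later evaluations cover every disease site found at baseline, so the text conflicts with itself. A positive MIBG must be repeated at each evaluation, except after two consecutive negative scans in a confirmed responder. That exception is in 7.2.1 only; Table 7-1 does not carry it.

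**Response criteria.** Appendix 5, Table 2-2 defines a non-target response of UNK as: "Progression has not been documented and one or more non-target lesions have not been assessed". In Table 2-3, target CR, PR or SD with non-target UNK gives overall UNK. The rule below the table, which yields UNK whenever there is no PD, begins: "If the evaluation of any of the target or non-target lesions identified at baseline could not be made during follow-up, the overall status must be".

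**Analysis rules.** SAP 2.6 requires two determinations of PR or better at least 4 weeks apart, and counts a best overall response (BOR) of UNK as non-response. SAP 5.4.1 defines a missing adequate assessment as "assessment not done or assessment with overall lesion response equal to UNK". In Appendix 5, section 3.2.7, only CR, PR or SD is an adequate assessment; if there is none, the start of treatment is used. Section 4.5.1 sets that duration to 1 day.

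**Lymphoma, for comparison.** Appendix 6, section 3.5.2 says: "For patients whose radiological response is anything other than CR, assessment of bone marrow, liver, spleen and B-symptoms will not be required".

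**The concern.** Each rule is reasonable alone, but together they penalise a site for using an option that the protocol gives it. A marrow-positive patient whose target lesions shrink by 30% or more, and whose marrow is not repeated, has no visit that Table 2-3 allows to be called PR. The lymphoma guideline avoids this by using marrow only when a CR is in question. The neuroblastoma text has no matching derivation rule, and SAP Table 4-1, which lists changes to the BOR rules, does not supply one.

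Neuroblastoma is the only group with declared ORR categories (Protocol 10.7.3) and a rule of 5 responses in 25 (Protocol 10.10.2). An assessability problem there bears directly on whether activity is declared. The same UNK visits also feed the PFS and DOR censoring rules.

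**Working it through.** **1. The plan's own figures.** With n = 25 and activity declared at 5 or more responses, the exact binomial gives P(X ≥ 5 | 0.10) = 0.0980 and P(X ≥ 5 | 0.30) = 0.9095. These match the stated 9.8% and 91.0%. The arithmetic is right, but it assumes that every true response can be scored.

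**2. Best overall response.** Day 15 of cycle c is study day (c − 1) × 21 + 15, so C2, C4, C6 and C10 fall on days 36, 78, 120 and 204. Take a patient with marrow positive at screening and not repeated, target PR at C2, C4 and C6, and PD at C10, scored as Appendix 5 is written:

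| Visit | Target | Non-target | Overall |
|---|---|---|---|
| C2, C4, C6 | PR | UNK | UNK |
| C10 | PD | any | PD |

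There is no PR determination and no SD or better. PD comes after day 85, so BOR is UNK; PD by day 85 would make it PD. Either way the patient is a non-responder. One repeat marrow does not rescue the response, because confirmation needs two assessable visits.

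**3. PFS.** If every post-baseline visit before the event is UNK, the last adequate date is day 1. SAP 5.4.1 sets D2 for the early schedule at 2 × 6 + 2 = 14 weeks.
- PD at C4D15: 78 − 1 = 77 days = 11 weeks, below D2, so it counts as an event.
- PD at C6D15: 120 − 1 = 119 days = 17 weeks, above D2, so it is censored at day 1. A scan 7 days early (16 weeks) is still above D2.
- No event: censored at day 1.

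**4. Illustration of size.** Let u be the share of true responders scored UNK because marrow was not repeated. The documents do not give u; the values below are assumed. The countable ORR is 0.30 × (1 − u).

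| u | Countable ORR | P(at least 5 of 25) |
|---|---|---|
| 0 | 30.0% | 91.0% |
| 10% | 27.0% | 84.5% |
| 20% | 24.0% | 75.2% |
| 50% | 15.0% | 31.8% |

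At a true ORR of 10%, the false-positive probability falls from 9.8% to 6.9% (u = 10%) or 0.7% (u = 50%).

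**5. MIBG omitted under the two-negative rule.** An omitted scan of a baseline-positive site also gives UNK. The rule applies only after a confirmed CR or PR, so ORR cannot change. For PFS and DOR, the same D2 formula applied to the later schedule gives 2 × 12 + 2 = 26 weeks (every 4 cycles after C6) and 2 × 18 + 2 = 38 weeks (every 6 cycles after C14). PD at the first omitted visit, 12 or 18 weeks after the last scanned visit, still counts. If the last MIBG is at C6, with omissions at C10 and C14 and PD at C20, the gap is 14 × 21 = 294 days = 42 weeks. That exceeds 38 weeks, so the patient is censored at C6.

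**The case against.** The strongest reply is that response is the local investigator's (Protocol 7.2.1, 10.7.3; SAP 2.6). Appendix 5, section 4.4 recognises that an unevaluated lesion makes the overall response UNK, allows such assessments to be re-evaluated, and says the investigator's assessment is not overridden. An investigator who records PR therefore keeps it. This stands, and it defeats the reading that marrow-positive patients can never be counted as PR. It does not settle the matter. Recording PR departs from Table 2-3, which SAP 5.4 adopts as governing, and section 4.4 gives no criterion for re-evaluation. Two sites with identical patients can return PR and UNK.

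Second, Protocol 7.2.1 says all baseline sites are evaluated later, so a site can comply with everything by repeating marrow. That is true, but Table 7-1 and the next sentences of 7.2.1 permit the opposite.

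Third, Protocol 7.1.3, 7.2.1 and Table 7-1 treat neuroblastoma and lymphoma alike in tying repeat marrow to a radiological CR. The intent may already be that marrow only qualifies a CR. That is plausible, but only the lymphoma guideline says how an unassessed marrow enters a PR or SD.

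Fourth, ORR is secondary in a phase 1 DLT study, the Group 1 result is called preliminary, and the bias would be toward understating activity. This stands and lowers the priority.

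Fifth, patients with non-target disease only can respond only by CR, and Table 7-1 then calls for marrow, so their response status is not lost. This also stands: the loss falls on patients with measurable disease and a PR.

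**Conclusion.** The point holds as a conflict between the assessment schedule and the response criteria. It leaves neuroblastoma ORR open to site-by-site reading and possibly biased downward. It should be fixed, but it does not touch the primary objective.

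A reader might infer three stronger things that the documents do not support:
- That marrow-positive patients cannot be PR. An investigator-recorded PR stands.
- That power is in fact 75% or 32%. Those values rest on an assumed share of true responders scored UNK; no marrow-positive, repeat-marrow or recording rate is given, and the share could be near zero.
- That such patients are generally censored at day 1. This needs every post-baseline visit before the event to be UNK, and PD within D2 still counts.

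The MIBG effect is secondary. It cannot alter ORR, and it alters PFS and DOR only through censoring.

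**What to change.** 1. Reconcile Protocol 7.2.1, Table 7-1, Protocol 10.7.3 with SAP 2.6, and Appendix 5 Tables 2-2 and 2-3, so that the status of unrepeated marrow is the same in all of them.
2. Add to SAP 5.4.1, for neuroblastoma: marrow that was not assessed does not make a PR or SD visit UNK. The visit is derived from target lesions, imaged non-target lesions and new lesions. Marrow is used only to qualify a CR or to record new or recurrent involvement as PD, as Appendix 6, section 3.5.2 does for lymphoma.
3. Where MIBG is omitted as 7.2.1 permits, carry the last negative status forward, and align Table 7-1 with that exception.

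The cost is wording and a small change to the response derivation, with no new procedure. The downside should be named in the report: PR and SD in these patients rest on imaging without marrow confirmation, and MIBG status at omitted visits is assumed, not observed. The rule should be set before database lock, since choosing it with results in view would invite bias.
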